Description of the cognitive training program, including principles and mechanisms
Participant ratings (1-10) of importance of cognitive training and confidence in ability to learn, to assess motivation and promote change talk
Ending interview 1 (summary, perceived impact, readiness for change)
MI Session 2 (~45-60 min)
Summary of previous session's content, emphasizing motivation to change (i.e. improve cognition)
Hands-on demonstration of cognitive training program
Constructing a decisional balance for participating in cognitive training, collaboratively problem-solving potential obstacles; filling out checklist to select reasons participants may want to do cognitive training
Filling out and discussing the patient's change plan (as pertains to cognition), highlighting cognitive training goals, identifying and collaboratively problem solving around obstacles, and eliciting level of commitment for change (i.e. improving cognition)
Ending interview 2 (summary of decisional balance and change plan)
Monthly MI Boosters (~ 20-30 min each)
Open-ended discussion of participant's views of how the training is progressing (whether helpful, perceived barriers, perceived progress, etc.)
Personal feedback on cognitive training task progress since last assessment
Participant ratings (1-10) of importance of continuing cognitive training and confidence in ability to learn (to assess motivation and promote change talk)
Constructing a decisional balance for participating in cognitive training, collaboratively problem-solving potential obstacles; filling out checklist to select reasons participants may want to continue to attend cognitive training
Ending MI Booster (summary, readiness to change/continue training, decisional balance, change plan)

Table 2. CI Intervention Elements

CONTROL INTERVIEW (CI) SESSIONS
Note: throughout both CI sessions, interviewer presents self as expert providing feedback to participant; interviewer avoids open-ended questions, affirmations, reflections, summaries, expressing empathy, etc.
CI Session 1 (~45-60 min)
Opening remarks, focus of sessions on finding out how the participant best learns new information
Completing learning style questionnaires (Achievement Motivation Profile)
Ending interview 1 (participant informed that s/he will receive feedback on learning styles during 2nd interview session)
CI Session 2 (~45-60 min)
Opening remarks (explanation of information provided by learning style questionnaires and how it may be helpful)

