Personal feedback on learning styles inventories (Achievement Motivation Profile)
Description of the cognitive training program, including principles and mechanisms
Hands-on demonstration of cognitive rehabilitation program
Ending interview 2 (summary of learning styles and opportunity for questions)
Monthly Sham CI Boosters (~ 20-30 min each)
Review of individual training exercises, soliciting participant opinion of whether they like or do not like specific tasks and how they might change the training
Interventionist provides rationale for presence/types of training tasks included and current training structure (emphasis on why current training should not be modified)

Data Analysis for primary aim:

Treatment adherence. Differences between MI and CI conditions on the total number of sessions attended over the 4 month cognitive rehabilitation (CR) phase were compared using Wilcoxon rank-sum test. As the total number of sessions attended followed a Poisson distribution, and as a considerable portion of the participants did not attend any sessions, zero-inflated Poisson (ZIP) model was built to evaluate treatment adherence, with the probability of not attending any sessions based on results of a logistic regression, and the number of sessions attended between conditions based on results of a Poisson regression.

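### The ZIP count part in effect compares only participants who started training, starting is something MI aims to change, and no effect on sessions per randomised person is planned

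*Combined protocol and SAP*

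**What the plan says.** The opening of the Study Protocol makes adherence to the training the primary outcome. The Treatment adherence paragraph, under the heading Data Analysis for primary aim, evaluates it in two ways. Total sessions in MI and CI "were compared using Wilcoxon rank-sum test". A ZIP model is then added because "a considerable portion of the participants did not attend any sessions". It has a zero part, "with the probability of not attending any sessions based on results of a logistic regression", and a count part, "the number of sessions attended between conditions based on results of a Poisson regression".

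This yields three results: Wilcoxon, starting and count. The paragraph does not rank them, does not name the analysis set, and does not say whether condition enters the zero part. It plans no difference or ratio of mean sessions over everyone randomised.

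Table 1 describes MI Session 2 as including "filling out checklist to select reasons participants may want to do cognitive training" and "eliciting level of commitment for change". Table 2 lists a description and demonstration of the program for CI Session 2, but neither of these elements.

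The analysis paragraph is in the past tense ("As the total number of sessions attended followed a Poisson distribution"; a ZIP "model was built to evaluate treatment adherence"), so it was written after the data had been seen.

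**The concern.** The count part is worded as a comparison between conditions, which invites reading its ratio as the effect of MI on attendance. But it draws on people who attended at least once, and that group forms after randomisation. The documents do not state outright that both interviews precede the first training session. The demonstration in Session 2 and the boosters from the end of month 1 imply it. If MI persuades additional people to start, the MI starters include a kind of person who, in CI, never appears among the starters, and the two groups are no longer comparable by randomisation.

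If the additional starters attend less than others, the ratio is pulled down even though MI has added sessions overall. If MI puts off people who would have attended little, the ratio is pulled up. The results that do respect randomisation do not say how many sessions MI adds.

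**Working it through.** **Inputs.** From the Study Protocol: about 120 participants randomised 1:1, so about 60 per arm, and at most 50 sessions. The share who never attended is described only as considerable, and the plan has no figure to reproduce. Assumed for illustration: 30% of CI never start; attenders average 25 sessions; MI adds 10 percentage points of starters; these extra starters average 8 sessions (16 and 25 as alternatives).

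**Step 1: whom the count part compares.** In a ZIP model the chance of zero sessions is π + (1−π)e^(−λ), and the chance of k > 0 sessions is (1−π)e^(−λ)λ^k/k!. With condition in both parts, each arm has its own π and λ. As long as zeros exceed what the Poisson part alone would produce, π absorbs the zeros and λ is set by starters only, through: starter mean = λ/(1−e^(−λ)). On simulated data with 60 per arm, the ZIP count ratio matched a starters-only zero-truncated Poisson ratio to four decimals at λ = 2, 3, 10 and 20.

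If the zero part has an intercept only, the two differ at low means (1.884 against 1.906 at λ = 2; 1.425 against 1.394 at λ = 3) and agree at 10 and 20. The reason is that Poisson zeros vanish quickly: e^(−2) = 13.5%, e^(−3) = 5.0%, e^(−8) = 0.03%.

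**Step 2: starter ratio against the ratio per randomised person.**

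CI mean per randomised person: 0.70 × 25 = 17.5.

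MI mean per randomised person: 0.70 × 25 × (1+g) + 0.10 × m, where g is the gain in people who would start under either condition and m is the mean of the extra starters.

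MI starter mean: the MI mean per randomised person divided by 0.80. The starter ratio is that figure divided by 25, which equals 0.70/0.80 = 0.875 times the ratio per randomised person.

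| m | g | MI mean per randomised person | Ratio per randomised person | MI starter mean | Starter ratio | Ratio in those starting either way |
|---|---|---|---|---|---|---|
| 8 | 0 | 17.5 + 0.8 = 18.3 | 1.046 | 22.875 | 0.915 | 1.00 |
| 16 | 0 | 17.5 + 1.6 = 19.1 | 1.091 | 23.875 | 0.955 | 1.00 |
| 25 | 0 | 17.5 + 2.5 = 20.0 | 1.143 | 25.0 | 1.00 | 1.00 |
| 8 | 10% | 19.25 + 0.8 = 20.05 | 1.146 | 25.06 | 1.00 | 1.10 |
| 16 | 10% | 19.25 + 1.6 = 20.85 | 1.191 | 26.06 | 1.04 | 1.10 |

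In the first row the starter ratio points against MI although MI adds 0.8 sessions per person. In the fourth it shows no effect, although those starting either way gain 10% and the arm as a whole gains 14.6%. Only when the extra starters attend like the others (third row) does the starter ratio recover the effect in those starting either way.

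**Step 3: the opposite direction.** Exchange the arms in the first row, so that MI deters those 10 points of low attenders. The starter ratio becomes 25/22.875 = 1.093, while the ratio per randomised person is 17.5/18.3 = 0.956.

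**Step 4: precision of a whole-arm mean difference.** With Poisson counts among attenders (first row), the CI variance is 0.70 × (25 + 625) − 17.5² = 148.75. The MI variance is 0.70 × 650 + 0.10 × (8 + 64) − 18.3² = 127.31. The standard error is √[(148.75 + 127.31)/60] = 2.14, giving a half-width of 1.96 × 2.14 = 4.2 sessions. Simulation gave 4.1 to 4.2, and 5.2 to 5.3 with over-dispersed counts. Bootstrap intervals covered the true value in 94.0% to 94.5% of simulated trials.

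**The case against.** **The whole-arm comparison is already there.** A reader might infer that the plan abandons the randomised comparison. It does not. The Wilcoxon test is listed first and appears to take total sessions with zeros included, and the logistic part compares starting across whole arms. The count ratio never stands alone. This is right, and it reduces the point to a missing effect size and an unlabelled conditional result.

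**Reversal needs two assumptions at once.** The extra starters must attend far less than others, and MI must do nothing for continuing attenders, although the boosters aim at continued attendance. With m = 8 and a robust standard error, the starter comparison was significant against MI in 34% of simulated trials without the 10% gain and in 1.8% with it. So a reader should not infer that the count part is likely to show MI as harmful. What survives is masking: with the gain, the starter ratio was significant for MI in 4% of trials, against 64% if extra starters attended like others.

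**Such percentages are not this plan's error rates.** The plan states no robust standard error. With the model-based Poisson one, the 34% becomes about 50%. With over-dispersed counts, the model-based test is significant against MI in about 20% of trials even when extra starters attend like others, which is a separate problem. The deterministic ratios in the table do not depend on this choice.

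**A mean difference should not displace the Wilcoxon test.** A reader might infer that the mean difference ought to decide. The documents do not support that: the analysis text postdates the data, and the Wilcoxon test is the documented whole-arm test. Nor does disagreement between the two force a choice. Their directions differed in 9% (m = 8) and 14% (m = 16) of simulated trials, against about 10% with no MI effect at all. When MI works both ways, the mean difference also has less power: 20% and 33%, against 34% and 39% for the Wilcoxon test.

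**Conclusion.** The point holds in a limited form. The count-part ratio is in effect a comparison among starters; starting follows randomisation and is targeted by MI; so the ratio is not a randomised effect and can mislead either way. No estimate per randomised person is planned beside the tests that do respect randomisation.

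Under the illustrative inputs, the starter ratio is 0.915 where the ratio per randomised person is 1.046, or 1.00 where it is 1.146. All start rates and session means behind these figures are assumed. The documents do not show that MI changed who started, so the actual direction and size cannot be stated. That the Wilcoxon test keeps the randomised comparison assumes that it includes everyone randomised, zeros included, which the text implies but does not say.

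**What to change.** - State that the Wilcoxon test on all randomised participants, zeros included, is the primary test of adherence.
- Beside it, as its effect size, report the MI minus CI difference in mean sessions per randomised person with a bootstrap 95% CI. The ZIP marginal mean ratio, (1−π)λ in MI over (1−π)λ in CI, can be added.
- Label this added estimate post hoc, and do not let it override the Wilcoxon test.
- Report the logistic part as the effect on starting. Label the Poisson count part as descriptive among starters, and do not rest the adherence conclusion on it.

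The cost is wording and one estimate from data already collected. The drawback is a wider interval: a half-width of about 4 to 5 sessions under the assumptions, against 2.2 to 2.6 for the starter difference (5.0 to 5.2 if over-dispersed). A true gain of 0.8 or 1.6 sessions would usually not be distinguished from zero. The estimate conveys size and uncertainty; it does not add power.
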